#### **4.7.1.2      Withdrawal from Study**

Every effort should be made to obtain information on healthy volunteers who withdraw from the study. The primary reason for withdrawal from the study should be documented on the appropriate eCRF.

Healthy volunteers will not be followed for any reason after consent has been withdrawn.

When a subject voluntarily withdraws from the study, or is withdrawn by the Investigator, samples collected until the date of withdrawal will be analyzed, unless the subject specifically requests for these to be discarded or local laws require their immediate destruction.

Healthy volunteers who withdraw from the study for safety reasons will not be replaced. Healthy volunteers who withdraw from the study for other reasons may be replaced.

#### **4.7.2 Study and Site Discontinuation**

The Sponsor has the right to terminate this study at any time. Reasons for terminating the study may include, but are not limited to, the following:

- The incidence or severity of adverse events in this or other studies indicates a potential health hazard to healthy volunteers.
- Healthy volunteer enrollment is unsatisfactory.
- Previously unknown data become available which raise significant concerns about the potential risk to participants from continuation of the study.

The Sponsor will notify the Investigator and Health Authorities if the study is placed on hold, or if the Sponsor decides to discontinue the study or development program.

The Sponsor has the right to replace a site at any time. Reasons for replacing a site may include, but are not limited to, the following:

- Excessively slow recruitment.
- Poor protocol adherence.
- Inaccurate or incomplete data recording.
- Non-compliance with the International Conference on Harmonisation (ICH) guideline for Good Clinical Practice.

### **5. ASSESSMENT OF SAFETY**

#### **5.1 SAFETY PARAMETERS AND DEFINITIONS**

Safety assessments will consist of monitoring and recording adverse events, including serious adverse events and non-serious adverse events of special interest; measurement of protocol-specified safety laboratory assessments; measurement of protocol-specified vital signs, ECGs; and other protocol-specified tests that are deemed critical to the safety evaluation of the study.

Certain types of events require immediate reporting to the Sponsor, as outlined in Section [5.4](#).

### **5.1.1        Adverse Events**

According to the ICH guideline for Good Clinical Practice, an adverse event is any untoward medical occurrence in a clinical investigation subject administered a pharmaceutical product, regardless of causal attribution. An adverse event can therefore be any of the following:

- Any unfavorable and unintended sign (including an abnormal laboratory finding), symptom, or disease temporally associated with the use of a medicinal product, whether or not considered related to the medicinal product.
- Any new disease or exacerbation of an existing disease (a worsening in the character, frequency, or severity of a known condition).
- Recurrence of an intermittent medical condition (e.g., headache) not present at baseline.
- Any deterioration in a laboratory value or other clinical test (e.g., ECG, X-ray) that is associated with symptoms or leads to a change in study treatment or concomitant treatment or discontinuation from study drug.
- Adverse events that are related to a protocol-mandated intervention, including those that occur prior to assignment of study treatment (e.g., screening invasive procedures such as biopsies).

### **5.1.2        Serious Adverse Events (Immediately Reportable to the Sponsor)**

A serious adverse event is any adverse event that meets any of the following criteria:

- Fatal (i.e., the adverse event actually causes or leads to death).
- Life-threatening (i.e., the adverse event, in the view of the Investigator, places the subject at immediate risk of death).

This does not include any adverse event that had it occurred in a more severe form or was allowed to continue might have caused death.

- Requires or prolongs inpatient hospitalization (see Section 5.3.5.9).
- Results in persistent or significant disability/incapacity (i.e., the adverse event results in substantial disruption of the healthy volunteer's ability to conduct normal life functions).
- Congenital anomaly/birth defect in a neonate/infant born to a mother exposed to study drug.
- Significant medical event in the Investigator's judgment (e.g., may jeopardize the healthy volunteer or may require medical/surgical intervention to prevent one of the outcomes listed above).

The terms “severe” and “serious” are not synonymous. Severity refers to the intensity of an adverse event (rated as mild, moderate, or severe, or according to a pre-defined grading criteria (see Section 5.3.3); the event itself may be of relatively minor medical significance (such as severe headache without any further findings).

Severity and seriousness need to be independently assessed for each adverse event recorded on the eCRF.

Serious adverse events are required to be reported by the Investigator to the Sponsor immediately (i.e., no more than 24 hours after learning of the event; see Section [5.4](#) for reporting instructions).

### **5.1.3 Non-Serious Adverse Events of Special Interest (Immediately Reportable to the Sponsor)**

Non-serious adverse events of special interest are required to be reported by the Investigator to the Sponsor immediately (i.e., no more than 24 hours after learning of the event; see Section 5.4 for reporting instructions). Adverse events of special interest for this study include the following:

- Cases of an elevated ALT or AST in combination with either an elevated bilirubin or clinical jaundice, as defined in Section 5.3.5.6.
- Suspected transmission of an infectious agent by the study drug, as defined below:

Any organism, virus, or infectious particle (e.g., prion protein transmitting transmissible spongiform encephalopathy), pathogenic or non-pathogenic, is considered an infectious agent. A transmission of an infectious agent may be suspected from clinical symptoms or laboratory findings that indicate an infection in a subject exposed to a medicinal product. This term applies only when a contamination of the study drug is suspected.

## 5.2 SAFETY PLAN

### **5.2.1 Management of Specific Adverse Events**

Flu-like symptoms: TLR7 agonists can be associated with dose-dependent flu-like symptoms. A percentage of healthy volunteers may develop fever, chills, fatigue, myalgia, malaise, and headache within several hours after the dosing with RO7020531. Symptomatic treatment is recommended in case these events occur.

No dose modification of RO7020531/placebo for safety reasons will be implemented in the MAD part of this study. At the discretion of the Investigator, study treatment can be discontinued. For the treatment stopping rules in individual healthy volunteers and dose escalation stopping rules, please see Section 3.1.3 and Section 4.7.1.1.

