The QOD schedule has been selected for the multiple dosing part of this study based on information acquired from non-clinical studies with RO7020531 and clinical studies with RO6864018, and is aimed to optimize PD responses while minimizing safety risks, such as poor tolerability with every day dosing.

Based on clinical data with another TLR7 agonist (Study ANA773-601), it is expected that priming of PD effects and tachyphylaxis to systemic IFN release provided by the QOD schedule might be a desirable effect that can potentially limit AEs, and improve tolerability and efficacy.

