## Appendix 1 Schedule of Assessments: SAD

Visit	Screening	Treatment Period					Follow Up Visit	Follow Up Call
		Day -1	Day 1	Day 2	Day 3	Day 5		
Day	D-28 to D-2						Day 8 a	Day 29 b
Informed Consent	x							
Eligibility	x	x						
Demography	x							
Medical History	x							
Physical Examination c	x	x					x	
Vital Signs d	x	x	7	2	x		x	
ECG-12 lead e	x	x	7	x	x		x	
Plasma PK Sample			12	2	x			
Urine PK Sample			5	x				
PD for Protein Biomarkers		x	4	x	x f	x f	x	
Whole Blood for RNA		x	4	x			x	
Hematology, Blood Chemistry, Coagulation, Urinalysis	x	x		x			x	
Pregnancy Test g	x	x					x	
Administration of Study Medication h			x					
Randomisation			x					
Autoimmune panel, Thyroid Function	x							
Viral Serology (HAV, HBV, HCV, HIV)	x							
Follicle Stimulating Hormone i	x							
Substance Use j	x	x						
In-Clinic Stay k		x	x	x	x			
Ambulatory Visit	x						x	x
Clinical Genotyping l			x					
Adverse Events m	x m	x m	x	x	x	x	x	x
Previous and Concomitant Treatments	x	x	x	x	x	x	x	x

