### Appendix 3 Schedule of Assessments: MAD

Visit	Screening	Treatment Period															Follow Up Visit	Follow Up Call
Day	D-28 to D-2	Day -1	Day 1	Day 2	Day 3	Day 4	Day 5	Day 6	Day 7	Day 8	Day 9	Day 10	Day 11	Day 12	Day 13	Day 14	Day 20 a	Day 41 b
Informed Consent	X																	
Eligibility	X	X																
Demography	X																	
Medical History	X																	
Physical Examination c	X	X								X							X	X
Vital Signs d	X	X	6	X	4	X	2	X	2	X	2	X	2	X	6	X	X	
ECG-12 lead e	X	X	6		3				X						6		X	
Plasma PK Sample			12	X	3	X	3	X	3	X	3	X	3	X	12	X		
PD for Protein Biomarkers		X	4	X	3	X	3	X	3	X					3	X	X	
Whole Blood for RNA		X	4	X	3	X	3	X	3	X					3	X	X	
Hematology, Blood Chemistry, Coagulation, Urinalysis	X	X				X				X			X		X	X	X	
Pregnancy Test f	X	X															X	
Administration of Study Medication g			X		X		X		X		X		X		X			
In-Clinic Stay h		X	X	X	X	X	X	X	X	X	X	X	X	X	X	X		
Ambulatory Visit	X																X	
Randomisation			X															
Autoimmune panel, Thyroid function	X																	
Viral Serology ( HAV, HBV, HCV, HIV)	X																X	
Follicle Stimulating Hormone i	X																	
Substance Use j	X	X																
Clinical Genotyping k			X															
Adverse Events	X l	X l	X	X	X	X	X	X	X	X	X	X	X	X	X	X	X	
Previous and Concomitant Treatments	X	X	X	X	X	X	X	X	X	X	X	X	X	X	X	X	X	

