## Appendix 4 Schedule of Assessments: MAD Detailed

Period	Day	Scheduled Time (h)	Vital Signs a	ECG-12 lead b	Hematology, Blood Chemistry, Coagulation, Urinalysis	Plasma PK Sample c	PD for Protein Biomarkers d	Whole Blood for RNA d	Clinical Genotyping e	Administration of Study Medication f
	Day -1		x	x	x		x	x		
Treatment Period	Day 1	Predose	x	x		x	x	x	x	
		0								x
		0.25				x				
		0.5	x	x		x				
		1	x	x		x				
		1.5				x				
		2	x	x		x	x	x		
		3				x				
		4	x	x		x				
		6				x	x	x		
		8				x				
		12	x	x		x	x	x		
		18				x				
	Day 2	24	x			x	x	x		
	Day 3	Predose	x	x		x	x	x		
		0								x
		2	x	x		x	x	x		
		4	x	x						
	Day 4	6	x			x	x	x		
		24	x		x	x	x	x		
		Predose	x			x	x	x		
	Day 5	0								x
		2				x	x	x		
		6	x			x	x	x		
	Day 6	24	x			x	x	x		
	Day 7	Predose	x	x		x	x	x		
		0								x
		2				x	x	x		
	Day 8	6	x			x	x	x		
		24	x		x	x	x	x		
		Predose	x			x				
	Day 9	0								x
		2				x				
		6	x			x				
	Day 10	24	x			x				
	Day 11	Predose	x		x	x				
		0								x
		2				x				
	Day 12	6	x			x				
		24	x			x				
		Predose	x	x	x	x	x	x		
	Day 13	0								x
		0.25				x				
		0.5	x	x		x				
		1	x	x		x				
		1.5				x				
		2	x	x		x	x	x		
		3				x				
		4	x	x		x				
		6				x	x	x		
		8				x				
		12	x	x		x				
		18				x				
	Day 14	24	x		x	x	x	x		
Follow Up Visit	Day 20 g		x	x	x		x	x		

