## Appendix 4 Schedule of Assessments: MAD Detailed (cont.)

- a) Vital signs include blood pressure, pulse rate, respiratory rate and body temperature. Blood pressure, respiratory rate and pulse rate will be obtained after the subject has been in a supine *or sitting* position for at least 5 minutes. Blood pressure measurement will be performed in triplicate (can be as short as 20-second to 1-minute interval between measurements). Pulse rate and body temperature measurement will be performed as single assessments.
- b) 12-lead ECGs will be obtained in triplicate (three consecutive interpretable 12-lead ECGs within a 2-5 minute interval) after the subject has been in a supine position for at least 10 minutes. Automated ECG intervals (PR (PQ), QRS, QT, QTcF) and HR will be captured or calculated, and the changes in T-wave and U-wave morphology will be documented.
- c) Plasma PK samples will be collected: pre-dose and 0.25, 0.5, 1, 1.5, 2, 3, 4, 6, 8, 12, 18 and 24 post-dose from Day 1 to Day 2 and from Day 13 to Day 14. On Days 3, 5, 7, 9, and 11, samples for PK will be taken at pre-dose and 2, 6 and 24 hours post-dose.
- d) PD samples will be collected: pre-dose and 2, 6, 12 and 24 post-dose from Day 1 to Day 2. On Days 3, 5, 7 and 13 samples for PD will be taken at pre-dose and 2, 6 and 24 hours post-dose. PD samples will be collected on follow-up visit.
- e) If the clinical genotyping blood sample is not collected at Day 1, it may be collected at any time during the conduct of the clinical study.
- f) Study drug will be administered in fasted state (after an overnight fast of at least 10 hours).
- g) A follow-up visit to be completed 7 days ( $\pm 1$ ) after the last dose of study medication.

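### MAD doses 1 and 7 have no 6 h vital signs, unlike the SAD dose and MAD doses 2-6, so nothing is scheduled from 4 to 12 h and no same-day post-dose time is shared with doses 3-6

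*Combined protocol and SAP*

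**What the plan says.** Section 5.2.1 describes dose-dependent flu-like symptoms as a feature of TLR7 agonists: "A percentage of healthy volunteers may develop fever, chills, fatigue, myalgia, malaise, and headache within several hours after the dosing with RO7020531". Section 1.2.1 adds that monkeys showed reversible heart-rate increases and a rise in body temperature. Safety and tolerability are the primary objective (Section 2.1). The incidence of vital-sign abnormalities, with pulse rate and temperature named, is a safety outcome (Section 3.3.1). Vital signs also feed MAD escalation (Section 3.1.2) and the stopping rules (Section 3.1.3).

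Footnote a of Appendix 4 defines the set: "Vital signs include blood pressure, pulse rate, respiratory rate and body temperature".

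The summary schedules give the number of sets per day. Appendix 1 (SAD) reads "Vital Signs d x x 7 2 x", which is seven on Day 1. Appendix 3 (MAD) reads "Vital Signs d X X 6 X 4 X 2 X 2 X 2 X 2 X 6 X X", which is 6, 4, 2, 2, 2, 2 and 6 on the seven dosing days.

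The detailed schedules give the times. In Appendix 2 the 6 h row of the SAD has vital signs and an ECG. In Appendix 4 the 6 h row on Days 1 and 13 has PK, protein and RNA samples, but its vital-sign and ECG cells are blank. Footnote c of Appendix 4 confirms the blood draw, with PK sampling at "pre-dose and 0.25, 0.5, 1, 1.5, 2, 3, 4, 6, 8, 12, 18 and 24 post-dose from Day 1 to Day 2" and the same times from Day 13 to Day 14.

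**The concern.** The named risk is fever and related symptoms some hours after dosing. After the first and last MAD doses the schedule stops measuring temperature and pulse at 4 h and resumes at 12 h. The SAD divides that interval with a 6 h reading. For doses 3 to 6 the 6 h reading is the only same-day post-dose one, and it has no counterpart after doses 1 and 7.

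Two things are at stake. An observed incidence of vital-sign abnormalities depends on when one looks, so a short-lived change without symptoms could go unrecorded after the first repeat-dose administration. Change over the course is also of interest: Section 3.2.1 expects priming and then tachyphylaxis under every-other-day dosing, which "might be a desirable effect that can potentially limit AEs, and improve tolerability and efficacy". A descriptive look at temperature or pulse across all seven doses needs a common post-dose time, and at present only 24 h serves. Nor can vital signs be paired at 6 h with the protein and RNA samples on Days 1 and 13, as they can on Days 3, 5 and 7.

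**Working it through.** **Step 1. Reproduce the plan's own counts.** The vital-sign marks were read row by row from Appendices 2 and 4 and compared with the day counts in Appendices 1 and 3. Each count is one pre-dose set plus the same-day post-dose sets.

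| Dose | Day | Same-day post-dose times (h) | Count from detailed table | Count in summary table |
|---|---|---|---|---|
| SAD | 1 | 0.5, 1, 2, 4, 6, 12 | 1 + 6 = 7 | 7 |
| MAD 1 | 1 | 0.5, 1, 2, 4, 12 | 1 + 5 = 6 | 6 |
| MAD 2 | 3 | 2, 4, 6 | 1 + 3 = 4 | 4 |
| MAD 3-6 | 5, 7, 9, 11 | 6 | 1 + 1 = 2 each | 2 each |
| MAD 7 | 13 | 0.5, 1, 2, 4, 12 | 1 + 5 = 6 | 6 |

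Every count agrees, so the blank 6 h cells on Days 1 and 13 are not an effect of how the table was read. In Appendix 4 as extracted, one 6 h row is printed beside Day 4. It belongs to the Day 3 dose, because Day 3 needs it to reach its count of 4. All seven MAD doses also have a 24 h set on the following day.

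**Step 2. Length of the interval.** After MAD doses 1 and 7: 12 - 4 = 8 h without a scheduled set. After the SAD dose the same span is split into 6 - 4 = 2 h and 12 - 6 = 6 h.

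**Step 3. Times shared between doses.**

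- Dose 1 or 7 with any of doses 3-6: {0.5, 1, 2, 4, 12} ∩ {6} is empty. Only pre-dose and 24 h are shared.
- Dose 1 or 7 with dose 2: {0.5, 1, 2, 4, 12} ∩ {2, 4, 6} = {2, 4}, plus pre-dose and 24 h.
- Dose 1 with dose 7: identical schedules, so all times are shared.
- Doses 2 to 6 with one another: 6 h, plus pre-dose and 24 h.

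**Step 4. Effect of adding 6 h on Days 1 and 13.** The count becomes 6 + 1 = 7 on each day, matching SAD Day 1. The longest scheduled interval between 4 and 12 h falls from 8 h to 6 h. The 6 h reading becomes common to the SAD dose and all seven MAD doses.

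**Step 5. Size of the addition.** Two sets per subject, with 20 to 30 MAD subjects (Section 6.1): 2 × 20 = 40 to 2 × 30 = 60 sets.

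**The case against.** The case for leaving the schedule alone has real content, and most of it limits how far the point can be pressed.

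- **Volunteers are not unobserved.** A reader might infer that a change between 4 and 12 h would come to light only if the volunteer complained. Section 5.3.1 does not support that: investigators ask about adverse events at every contact, and events noticed by staff are recorded too. Blood draws at 6 h and 8 h put two contacts inside the interval, and further checks can be made if needed. A rise that begins by 4 h or lasts to 12 h is measured anyway. What remains is that prompted readings are not systematic data.
- **The main comparisons exist.** A reader might infer that doses 1 and 7 cannot be compared with the rest at all. In fact pre-dose and 24 h are common to every dose. Priming is described as an effect of the second dose, and doses 1 and 2 share 2 h and 4 h. First and last doses match at every time. Only doses 1 and 7 against doses 3-6 lack a same-day post-dose match.
- **No planned analysis needs the match.** Section 6.5.3 provides flagged listings, with tabular summaries as appropriate. The priming and tachyphylaxis of Section 3.2.1 concern PD response and systemic IFN, and PD is sampled at 6 h on Days 1 and 13.
- **No peak is placed at 4 to 12 h.** The time course in Section 5.2.1 is unspecific and is already sampled at 0.5, 1, 2 and 4 h. The monkey findings in Section 1.2.1 carry no times. Days 1 and 13 are also the most densely monitored MAD days, while doses 3-6 have nothing scheduled for the 24 - 6 = 18 h after their 6 h reading.
- **The SAD gives a first-dose 6 h reading**, from eight active volunteers per cohort. They are different people, possibly at a different dose, and they say nothing about a seventh dose.
- **Early experience is reassuring.** Section 1.2.2 reports only mild events, and no clinically significant vital-sign changes or trends, after single doses up to 170 mg in the global study.

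None of this gives a reason for omitting the reading at a time when blood is already drawn, and the documents state none.

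**Conclusion.** The point holds as a gap in scheduled measurement. After MAD doses 1 and 7 no vital signs are scheduled for 8 h, and neither dose shares a same-day post-dose time with doses 3 to 6. The loss is limited to temperature, pulse, respiratory-rate or blood-pressure changes that are symptom-free and confined to 4 to 12 h, and to the descriptive comparison of those two doses with the middle four.

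A reader might go further and conclude that the MAD safety assessment is unsound or that its escalation decisions lack a basis. The documents do not support that. Adverse events are actively sought, the first- and last-dose schedules match, and no planned analysis depends on the missing time. The conclusion assumes that a blank cell means no scheduled reading, which the matching counts bear out. It makes no assumption about when any effect peaks, because the documents do not say. This is a modest, inexpensive improvement to primary-objective data.

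**What to change.** In Appendix 4, mark vital signs at 6 h on Days 1 and 13. In Appendix 3, change the vital-sign counts for those two days from 6 to 7. Both then agree with the SAD schedule in Appendices 1 and 2. The existing footnote already includes temperature, and Section 4.6.1 already places vital signs before post-dose blood sampling, so no other text need change.

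The cost is two non-invasive sets per MAD subject, about 40 to 60 sets in total, taken while the volunteer is in the unit for the 6 h draw: a few minutes of site time and one table edit in each appendix. Dosing and treatment are untouched. The change leaves 6 to 12 h without a scheduled reading after doses 1 and 7, as in the SAD, and does not alter the schedule after doses 3 to 6.

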## **5.3 METHODS AND TIMING FOR CAPTURING AND ASSESSING SAFETY PARAMETERS**

The Investigator is responsible for ensuring that all adverse events (see Section 5.1.1 for definition) are recorded on the Adverse Event eCRF and reported to the Sponsor in accordance with instructions provided in this section and in Section 5.5 to Section 5.7.

For each adverse event recorded on the Adverse Event eCRF, the Investigator will make an assessment of seriousness (see Section 5.1.2 for seriousness criteria), severity (see Section 5.3.3), and causality (see Section 5.3.4).

### **5.3.1 Adverse Event Reporting Period**

Investigators will seek information on adverse events at each healthy volunteer contact. All adverse events, whether reported by the healthy volunteer or noted by study personnel, will be recorded in the healthy volunteer's medical record. Adverse events will then be reported on the Adverse Event eCRF as follows:

**After informed consent** has been obtained **but prior to initiation of study drug**, only serious adverse events caused by a protocol-mandated intervention should be reported (e.g., serious adverse events related to invasive procedures such as biopsies). Any other adverse event should not be reported.

**After initiation of study drug**, all adverse events, regardless of relationship to study drug, will be reported until 28 days after the last dose of study drug.

**After a period of** 28 days from the last dose of study drug, Investigators should report any deaths, serious adverse events, or other adverse events of concern that are believed to be related to prior treatment with study drug (see Section 5.6).

### **5.3.2 Eliciting Adverse Event Information**

A consistent methodology of non-directive questioning should be adopted for eliciting adverse event information at all healthy volunteer evaluation time-points. Examples of non-directive questions include the following:

“How have you felt since your last clinic visit?”

“Have you had any new or changed health problems since you were last here?”

### **5.3.3 Assessment of Severity of Adverse Events**

Table 2 provides guidance for assessing adverse event severity.

